4.3 Assignment of UPN

Each patient will be identified with a unique patient number (UPN) for this study. All data will be recorded with this identification number on the appropriate CRFs.

5.0 TREATMENT PLAN

5.1 Premedication Administration

Consider prophylactic or therapeutic administration of 0.25 to 1 mg of IV or SC atropine to prevent early diarrhea (occurring during or shortly after infusion of irinotecan).

It is recommended that patients receive premedication with antiemetic agents on the day of treatment, starting at least 30 minutes before administration of irinotecan. Suggested antiemetic agents are 10 mg of dexamethasone given with a 5HT3 blocker (e.g. ondansetron or granisetron).

Prior to each ramucirumab infusion, premedicate all patients with an intravenous histamine H1 antagonist (e.g., diphenhydramine). For patients who have experienced a grade 1 or 2 infusion-related reaction, also premedicate with dexamethasone (or equivalent) and acetaminophen prior to each ramucirumab infusion.

5.2 Agent Administration

Patients will receive ramucirumab intravenously on an outpatient basis at a dose of 8 mg/kg over the course of 60 minutes on Day 1 of each 14-day cycle. They will then receive irinotecan intravenously at a dose of 180 mg/m² over the course of 90 minutes on Day 1 of each 14-day cycle. With approval by the Washington University PI, the agents may be given on different days within the protocol specified window.

5.3 Evaluability

All patients who receive any study treatment are evaluable for toxicity. Patients are evaluated from first receiving study treatment until a 30-day follow up after the conclusion of treatment or death.

All patients are evaluable for disease response unless they discontinue treatment prior to completion of Cycle 4 and have not had any disease assessment.

5.4 General Concomitant Medication and Supportive Care Guidelines

Protocol Version: 10Jun2022 – Amendment 6 Page 19 of 64

Patients receiving warfarin must be switched to low molecular weight heparin and have achieved stable coagulation profile prior to the first dose of protocol therapy.

Do not administer strong CYP3A4 inducers or inhibitors while patients are receiving irinotecan (refer to Appendix B).

UGT1A1 inhibitors (atazanavir, gemfibrozil, indinavir) are prohibited.

Late diarrhea associated with irinotecan can be life-threatening since it may be prolonged and may lead to dehydration, electrolyte imbalance, or sepsis. Patients should have loperamide readily available to begin treatment for late diarrhea. Begin loperamide at the first episode of poorly formed or loose stools or the earliest onset of bowel movements more frequent than normal. One dosage regimen for loperamide is 4 mg at the first onset of later diarrhea and then 2 mg every 2 hours until the patient is diarrhea-free for at least 12 hours. Loperamide is not recommended to be used for more than 48 consecutive hours at these doses because of the risk of paralytic ileus.

Patients with unresected primary tumors (or local recurrence) who develop grade 3 or 4 venous thromboembolism may also receive anticoagulation and continue ramucirumab therapy provided that the tumor does not confer an excessive bleeding risk, in the opinion of the patient's physician.

5.5 Women of Childbearing Potential

Women of childbearing potential (defined as women with regular menses, women with amenorrhea, women with irregular cycles, women using a contraceptive method that precludes withdrawal bleeding, and women who have had a tubal ligation) are required to have a negative serum pregnancy test within 7 days prior to the first day of treatment.

Female and male patients (along with their female partners) are required to use two forms of acceptable contraception, including one barrier method, during participation in the study and for 3 months following the last dose of either study drug.

If a patient is suspected to be pregnant, ramucirumab and irinotecan should be immediately discontinued. In addition, a positive urine test must be confirmed by a serum pregnancy test. If it is confirmed that the patient is not pregnant, the patient may resume dosing.

If a female patient or female partner of a male patient becomes pregnant during therapy or within 3 months after the last dose of either study drug, the investigator must be notified in order to facilitate outcome follow-up.

5.6 Duration of Therapy

If at any time the constraints of this protocol are considered to be detrimental to the patient's health and/or the patient no longer wishes to continue protocol therapy, the protocol therapy should be discontinued and the reason(s) for discontinuation documented

Protocol Version: 10Jun2022 – Amendment 6 Page 20 of 64

in the case report forms.

In the absence of treatment delays due to adverse events, treatment may continue indefinitely or until one of the following criteria applies:

- Documented and confirmed disease progression
- Death
- Adverse event(s) that, in the judgment of the investigator, may cause severe or permanent harm or which rule out continuation of study drug, including:
 - o Grade 3 or 4 infusion reaction
 - o Grade 4 hypertension
 - o Grade 3 or 4 arterial thromboembolic event, or any PE/DVT occurring or worsening during anticoagulant therapy
 - One occurrence of urine protein level > 3 g/24 hours, three occurrences of urine protein level > 2 g/24, or urine protein level > 2 g/24 hours for more than 2 weeks
 - o Gastrointestinal perforation or fistula formation
 - o RPLS
 - Hepatic encephalopathy or other serious signs of liver impairment such as hepatorenal syndrome
- General or specific changes in the patient's condition render the patient unable to receive further treatment in the judgment of the investigator
- Suspected pregnancy
- Serious non-compliance with the study protocol
- Lost to follow-up
- Patient withdraws consent
- Investigator removes the patient from study
- The Siteman Cancer Center decides to close the study

Patients who prematurely discontinue treatment for any reason will be followed as indicated in the study calendar.

5.7 **Duration of Follow-up**

Patients will be followed every 2 months after discontinuation of treatment for progression and survival for 30 months. Patients removed from study for unacceptable adverse events will be followed until resolution or stabilization of the adverse event.

6.0 DOSE DELAYS/DOSE MODIFICATIONS

6.1 Dose Modifications for Ramucirumab

Treatment modifications for toxicities not listed below will be made at the discretion of the PI. Treatment may be held for a maximum of 4 weeks before a patient must be removed from study treatment. Treatment may be held beyond 4 weeks at the discretion of the PI.

6.1.1 Infusion-Related Reactions

Reduce the infusion rate of ramucirumab by 50% for grade 1 or 2 infusion-related reactions. Permanently discontinue ramucirumab for grade 3 or 4 infusion-related reactions.

6.1.2 Hypertension

Interrupt ramucirumab for severe hypertension until controlled with medical management. Permanently discontinue ramucirumab for severe hypertension that cannot be controlled with antihypertensive therapy or any grade 4 hypertension.

6.1.3 Proteinuria

If urinalysis or dipstick shows protein $\geq 2+$, a 24-hour urine collection must be collected and ramucirumab cannot be dosed until the below criteria are met. Interrupt ramucirumab for urine protein levels ≥ 2 g/24 hours. Reinitiate treatment at a reduced dose once the urine protein level returns to < 2 g/24 hours. If the protein level ≥ 2 g/24 hours reoccurs, interrupt ramucirumab and reduce the dose again once the urine protein level returns to < 2 g/24 hours. Permanently discontinue ramucirumab for urine protein level > 3 g/24 hours, if there is a third occurrence of > 2 g/24 hours, if the protein level does not return to < 2 g/24 hours within 2 weeks, or in the setting of nephrotic syndrome. If it is anticipated that the urine protein will be elevated, a 24-hour urine collection can be collected and evaluated for dosing criteria independent of the urinalysis or urine dipstick.

Initial dose	8 mg/kg
First dose reduction	6 mg/kg
Second dose reduction	5 mg/kg

6.1.4 Venous and Arterial Thromboembolic Events, Gastrointestinal Perforation, Fistula, or Bleeding

Protocol Version: 10Jun2022 – Amendment 6 Page 22 of 64

Ramucirumab should be permanently discontinued in the event of a gastrointestinal perforation or fistula formation.

Patients with unresected primary tumors (or local recurrence) who develop grade 3 or 4 venous thromboembolism may receive anticoagulation and continue ramucirumab therapy provided that the tumor does not confer an excessive bleeding risk, in the opinion of the patient's physician.

Grade 3 or 4 arterial thromboembolic events, or any PE/DVT occurring or worsening during anticoagulant therapy, require permanent discontinuation of ramucirumab therapy. Any venous or arterial event leading to discontinuation of ramucirumab therapy will be considered serious and should be reported via the SAE mechanism.

For any clinically significant bleeding events deemed at least possibly related to Ramucirumab, patients must be discontinued from further treatment unless permission is granted from the Washington University PI to continue study therapy.

6.1.5 Hepatic Encephalopathy or Other Serious Signs of Liver Impairment

Permanently discontinue ramucirumab. Signs of serious liver impairment include hepatorenal syndrome or other signs as determined by the treating physician.

6.1.6 Reversible Posterior Leukoencephalopathy Syndrome

If RPLS is diagnosed, ramucirumab must be permanently discontinued. All cases of RPLS must be reported via the SAE mechanism.

6.2 Dose Modifications for Irinotecan

Treatment modifications for toxicities not listed below will be made at the discretion of the PI. Patients requiring a dose reduction beyond that outlined in the study protocol will have the agent discontinued. The other agent may be continued independently in keeping with the applicable dose modifications for that agent. Treatment may be held for a maximum of 4 weeks before a patient must be removed from study treatment. Treatment may be held beyond 4 weeks at the discretion of the PI.

Initial Dose	180mg/m^2
First Dose Reduction	150 mg/m^2
Second Dose Reduction	120 mg/m^2

6.2.1 Late Diarrhea

Treatment should be delayed until the return of pre-treatment bowel function for at least 24 hours without anti-diarrhea medication. Patients must not be treated with

Protocol Version: 10Jun2022 – Amendment 6 Page 23 of 64

irinotecan until resolution of any bowel obstruction. If grade 2, 3, or 4 late diarrhea recurs, subsequent doses of irinotecan should be decreased to 150 mg/m².

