6.2.2 Myelosuppression

Hold irinotecan if neutropenic fever occurs or if ANC $< 1000/\text{mm}^3$. After recovery to an ANC $\ge 1000/\text{mm}^3$, subsequent doses of irinotecan should be reduced by one level.

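### Section 6.2.1 fixes irinotecan at 150 mg/m² after recurrent late diarrhea, so a patient already at 150 gets no per-infusion reduction, although 6.2 lists a 120 level

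*Combined protocol and SAP*

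**What the plan says.** Section 5.2 starts every patient at the same dose: "They will then receive irinotecan intravenously at a dose of 180" mg/m², on Day 1 of each 14-day cycle. Section 6.2 then gives a three-step table: 180 initially, 150 at the first reduction, and 120 at the line labelled "Second Dose Reduction".

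The triggers for moving down the table are in the subsections, and they are worded differently:

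- **6.2.1 (late diarrhea)** requires a hold: "Treatment should be delayed until the return of pre-treatment bowel function for at least 24 hours without anti-diarrhea medication". It then sets the dose: "If grade 2, 3, or 4 late diarrhea recurs, subsequent doses of irinotecan should be decreased to 150" mg/m².
- **6.2.2 (myelosuppression)** is relative: "subsequent doses of irinotecan should be reduced by one level".

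Two general sentences in 6.2 bear on the gap. One gives discretion: "Treatment modifications for toxicities not listed below will be made at the discretion of the PI". The other sets the end of the ladder: "Patients requiring a dose reduction beyond that outlined in the study protocol will have the agent discontinued".

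For ramucirumab, the proteinuria rule in 6.1.3 covers a repeat event explicitly: "interrupt ramucirumab and reduce the dose again once the urine protein level returns to" below 2 g/24 hours.

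**The concern.** The diarrhea rule names a destination, while the myelosuppression rule names a step. The two agree only for a patient still at 180. A patient reaches 150 by ordinary routes: one earlier diarrhea recurrence, or one episode of neutropenic fever or low neutrophil count. If diarrhea then recurs, an instruction to decrease to 150 changes nothing, and no sentence directs the move to 120 for this toxicity. The discretion sentence in 6.2 does not fill the gap, because it covers toxicities that are not listed and late diarrhea is listed. The other discretion given to the PI in 6.2 concerns how long treatment may be held, not the dose.

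What is at stake is the restart dose for a toxicity that Section 5.4 describes as potentially life-threatening. The trial runs at five institutions (15.1), toxicity and tolerability are a secondary objective (2.2), and 1.6 says that, to the authors' knowledge, the regimen had not been given to this population before. Sites that restart at different doses after the same event would treat patients differently and make the tolerability results harder to interpret.

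**Working it through.** The plan states no figure to reproduce here. The check applies each rule to each dose level.

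**Inputs.** Dose levels 180, 150 and 120 mg/m² (6.2 table; starting dose also in 5.2). Diarrhea target 150 mg/m² (6.2.1). One-level rule (6.2.2, used as the comparator). Cycle length 14 days, extendable to 21 (10.0).

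**Step 1: reduction per infusion = (current − new) / current.**

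| Current dose | Literal 6.2.1 | One-level rule |
|---|---|---|
| 180 | to 150: (180 − 150)/180 = 16.7% | to 150: 16.7% |
| 150 | stays 150: (150 − 150)/150 = 0% | to 120: (150 − 120)/150 = 20.0% |
| 120 | target 150 is 150/120 = 1.25 times the current dose, so it is not a decrease | no listed level remains; discontinue under 6.2 |

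The 120 level cannot be reached through the diarrhea rule as worded.

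**Step 2: dependence on order.** Take one patient with the same two events.

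- Recurrent diarrhea, then neutropenia: 180, 150, 120. Total reduction (180 − 120)/180 = 33.3%.
- Neutropenia, then recurrent diarrhea: 180, 150, 150. Total reduction (180 − 150)/180 = 16.7%.

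The final dose is 150/120 = 1.25 times as high in the second order. The documents give no clinical reason for the difference.

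**Step 3: other routes to lower exposure.** Section 10.0 lets the physician lengthen a cycle from 14 to as many as 21 days. In weekly dose intensity:

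- 150 every 14 days: 150/2 = 75 mg/m²/week
- 150 every 21 days: 150/3 = 50 mg/m²/week, or (75 − 50)/75 = 33.3% less
- 120 every 14 days: 120/2 = 60 mg/m²/week, or (75 − 60)/75 = 20.0% less

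Exposure over time can therefore be lowered within the protocol, by more than the 120 step would achieve, without stopping and without an exception. The extension does not lower the dose of any single infusion, and nothing in 6.2.1 ties it to diarrhea.

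**The case against.** The strongest answer is that the ladder already covers the case. It stands in 6.2, above all the toxicity subsections, and its lines are labelled by order. Since everyone starts at 180, 6.2.1 may simply name the first step for the usual patient and leave the next step to the table. Nothing in 6.2 reserves 120 for myelosuppression, and a site that keeps 150 at 150 is not decreasing anything. This reading is reasonable and probably reflects the intent. It remains an inference, though: the table lists levels, the subsections say when to use them, and the diarrhea subsection names only 150. Where the protocol wants a second step after a repeat event, as for proteinuria, it says so.

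The safeguards also count. There is no re-dosing until bowel function has recovered without medication (6.2.1), loperamide starts at the first loose stool (5.4), the cycle can be lengthened (10.0), the investigator may stop for adverse events (5.6), and ramucirumab may continue alone (6.2). A single-patient exception with prior approval is also available (7.1.1, Appendix C). These limit the harm, but none states the restart dose.

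A reader might infer two stronger things. One is that 6.2 forces irinotecan to be stopped when diarrhea recurs at 150. That is strained: the discontinuation sentence applies to a reduction beyond what the protocol outlines, and 120 is outlined in 6.2 itself. The other is that the protocol compels re-dosing at 150, or even an increase from 120. It does not: the rule says the dose should be decreased, which rules out an increase, and the routes above remain open.

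**Conclusion.** The point holds as a gap in a dosing rule, limited to patients already below 180 mg/m² whose grade 2 to 4 late diarrhea recurs. For a patient at 150, two readings are reasonable: stay at 150 (literal 6.2.1) or go to 120 (the general ladder in 6.2). The difference is 0% against 20% per infusion, and the same two toxicities can end at 150 or 120 depending on which came first. These figures rest only on the listed dose levels and on reading 6.2.1 literally.

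The documents give no rates of late diarrhea or dose reduction, so the number of patients affected is unknown and could be small. A reader might infer that the gap weakens the efficacy result, but the documents do not support this. No sample size or power input in 15.1 depends on irinotecan dose steps, the PFS definition in 15.2 does not refer to dose, and imaging stays on its 8-week schedule whatever the dosing delays (10.0, 12.1). The matter concerns patient safety and consistency between sites, and it should be corrected.

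**What to change.** Replace the last sentence of 6.2.1 with a relative rule that matches 6.2.2 and the 6.2 table, for example:

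> *On any recurrence of grade 2–4 late diarrhea, reduce later irinotecan doses by one dose level (180 to 150, or 150 to 120 mg/m²). Discontinue irinotecan if a dose below 120 mg/m² would be required.*

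This leaves the rule unchanged at 180, gives a defined step at 150 and a defined endpoint at 120, and makes the result independent of the order of events. If the sponsor instead means 150 to be the floor for diarrhea, 6.2.1 should say so and state what to do when diarrhea recurs there.

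The cost is one sentence in the next amendment, with no effect on sample size, data collection or analysis.

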6.2.2 Myelosuppression

Hold irinotecan if neutropenic fever occurs or if ANC $< 1000/\text{mm}^3$. After recovery to an ANC $\ge 1000/\text{mm}^3$, subsequent doses of irinotecan should be reduced by one level.

6.2.3 Hypersensitivity

Discontinue irinotecan if anaphylactic reaction occurs.

6.2.4 Pulmonary Toxicity

If Interstitial Pulmonary Disease is diagnosed, irinotecan and other chemotherapy should be discontinued and appropriate treatment instituted as needed.

7.0 REGULATORY AND REPORTING REQUIREMENTS

The entities providing oversight of safety and compliance with the protocol require reporting as outline below.

Please refer to Appendix C for definitions and Appendix D for a grid of reporting timelines.

Adverse events will be tracked from start of treatment through 30 days following the last day of study treatment. All adverse events must be recorded on the toxicity tracking case report form.

Refer to the data submission schedule in Section 11 for instructions on the collection of AEs in the EDC.

Reporting requirements for Washington University study team may be found in Section 7.1. Reporting requirements for secondary site study teams participating in Washington University-coordinated research may be found in Section 7.2.

Eli Lilly requires that all events be reported as outlined in Section 7.6.

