3.0 PATIENT SELECTION

3.1 Inclusion Criteria

- 1. Histopathologically or cytologically confirmed diagnosis of gastric or gastroesophageal junction (GEJ) adenocarcinoma that is metastatic or locally advanced and unresectable.
- 2. Measurable disease defined as lesions that can be accurately measured in at least one dimension (longest diameter to be recorded) as ≥ 10 mm with CT scan (or MRI at the discretion of the PI), as ≥ 20 mm by chest x-ray, or ≥ 10 mm with calipers by clinical exam.
- 3. Either primary or non-osseous metastatic site amenable for research biopsy for patients enrolled at Washington University, if safe and feasible, as confirmed by scheduling of biopsy procedure. Other methods to obtain appropriate cancer cells such as large-volume paracentesis or thoracentesis can be allowed at PI discretion. Biopsy or other procedures should be performed at least 7 days prior to C1D1.

Protocol Version: 10Jun2022 – Amendment 6 Page 14 of 64

- 4. Experienced documented objective radiographic or clinical disease progression during first-line therapy or within 4 months after the last dose of first-line therapy with any platinum/fluoropyrimidine doublet with or without anthracycline (epirubicin or doxorubicin) or taxane (docetaxel) for unresectable or metastatic disease.
 - NOTE: This is not intended to be an exclusive list of allowed agents. The targeted therapies such as Herceptin and ADC, or immunotherapies without cytotoxic chemotherapy, are permitted.
- 5. At least 18 years of age.
- 6. ECOG performance status ≤ 1 (see Appendix A).
- 7. Normal bone marrow and organ function as defined below:
 - a. Absolute neutrophil count (ANC) $\geq 1,500/\mu L$
 - b. Hemoglobin $\geq 9.0 \text{ g/dL } (5.58 \text{ mmol/L})$
 - c. Platelets $\geq 100,000/\mu L$
 - d. Total bilirubin $\leq 1.5 \text{ mg/dL} (25.65 \, \mu\text{mol/L})$
 - e. $AST(SGOT)/ALT(SGPT) \le 3.0 \text{ x IULN (or } \le 5.0 \text{ x IULN in the setting of liver metastases)}$
 - f. Creatinine ≤ 1.5 x IULN OR creatinine clearance ≥ 40 mL/min/1.73 m² for patients with creatinine levels > 1.5 x IULN (that is, if serum creatinine is > 1.5 x IULN, a 24-hour urine collection to calculate creatinine clearance must be performed)
 - g. Urinary protein \leq 1+ on dipstick or routine UA; if dipstick or routine UA is \geq 2+, a 24-hour urine collection for protein must demonstrate < 1000 mg of protein in 24 hours

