7.1.6 Timeframe for Reporting Required Events

Adverse events will be tracked for 30 days following the last day of study treatment. With the exception of progressive disease, all adverse events that occur between the first treatment on study and 30 days after the last day of study treatment will be recorded on the case report forms. This includes all adverse events that are CTCAE version 4.03 gradable laboratory values, regardless of attribution or clinical significance. Progressive disease should not be reported as an AE.

In addition to the planned revision to the protocol detailed above, please find guidance below for tracking of abnormal labs in the study EDC:

- For patients currently on treatment at the time this clarification is released, enter the highest occurrence of each gradable abnormal lab to date with drug attribution and the highest gradable abnormal labs with drug attribution per cycle moving forward (regardless of clinical significance) on the AE case report form.
- For patients off study at the time this clarification is released, enter the highest grade of each abnormal lab with drug attribution for the duration of the patient's time on study treatment on the AE case report form.
- Please note that medical history data is not required to be entered on the AE case reporting form.

Protocol Version: 10Jun2022 – Amendment 6 Page 27 of 64

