9.1.1 Collection of Specimens

For patients enrolled at Washington University School of Medicine, prior to study treatment, fresh tissue samples will be obtained either by surgical laparoscopic sampling (preferred), endoscopic biopsy, or image-guided core biopsy. If safe and feasible, biopsy will be done at least 7 days prior to planned C1D1. Additional methods to obtain adequate samples for PDX/PDO generation, including large-volume paracentesis or thoracentesis, will be allowed at PI discretion.

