11.1 Adverse Event Collection in the Case Report Forms

All adverse events that occur beginning with start of treatment (minus exceptions defined in Section 7.0) must be captured in the Toxicity Form. Baseline AEs should be captured on the Toxicity Form.

Participant death due to disease progression should be reported on the Toxicity Form as grade 5 disease progression. If death is due to an AE (e.g. cardiac disorders: cardiac arrest), report as a grade 5 event under that AE. Participant death must also be recorded on the Death Form.

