APPENDIX C: Definitions for Adverse Event Reporting

A. Adverse Events (AEs)

As defined in 21 CFR 312.32:

Definition: any untoward medical occurrence associated with the use of a drug in humans, whether or not considered drug-related.

Grading: the descriptions and grading scales found in the revised NCI Common Terminology Criteria for Adverse Events (CTCAE) version 4.03 will be utilized for all toxicity reporting. A copy of the CTCAE version 4.03 can be downloaded from the CTEP website.

Attribution (relatedness), Expectedness, and Seriousness: the definitions for the terms listed that should be used are those provided by the Department of Health and Human Services' Office for Human Research Protections (OHRP). A copy of this guidance can be found on OHRP's website:

http://www.hhs.gov/ohrp/policy/advevntguid.html

B. Suspected Adverse Reaction (SAR)

As defined in 21 CFR 312.32:

Definition: any adverse event for which there is a reasonable possibility that the drug caused the adverse event. "Reasonable possibility" means there is evidence to suggest a causal relationship between the drug and the adverse event. "Suspected adverse reaction" implies a lesser degree of certainty about causality than adverse reaction, which means any adverse event caused by a drug.

C. Life-Threatening Adverse Event / Life Threatening Suspected Adverse Reaction

As defined in 21 CFR 312.32:

Definition: any adverse drug event or suspected adverse reaction is considered "life-threatening" if, in the view of the investigator, its occurrence places the patient at immediate risk of death. It does not include an adverse event or suspected adverse reaction that, had it occurred in a more severe form, might have caused death.

D. Serious Adverse Event (SAE) or Serious Suspected Adverse Reaction

As defined in 21 CFR 312.32:

Definition: an adverse event or suspected adverse reaction is considered "serious" if, in the view of the investigator, it results in any of the following outcomes:

- o Death
- o A life-threatening adverse event

Protocol Version: 10Jun2022 – Amendment 6 Page 59 of 64

- o Inpatient hospitalization or prolongation of existing hospitalization
- A persistent or significant incapacity or substantial disruption of the ability to conduct normal life functions
- o A congenital anomaly/birth defect

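### Routine AE collection opens at the first dose, so complications of the earlier research biopsy are not reliably recorded or attributed

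*Combined protocol and SAP*

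**What the plan says.** **Collection window.** Section 7.0: "Adverse events will be tracked from start of treatment through 30 days following the last day of study treatment". Section 7.1.6 says that the case report forms take "all adverse events that occur between the first treatment on study and 30 days after the last day of study treatment", apart from progressive disease. Section 11.1 agrees: "All adverse events that occur beginning with start of treatment (minus exceptions defined in Section 7.0) must be captured in the Toxicity Form". The next sentence of Section 11.1, however, asks for baseline AEs on the same form. The Section 10.0 calendar, as extracted, shows an X for adverse event assessment in the Screening column.

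**Definition and population.** Appendix C defines an AE as "any untoward medical occurrence associated with the use of a drug in humans, whether or not considered drug-related". Section 5.3 states: "All patients who receive any study treatment are evaluable for toxicity".

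**The procedure.** For patients enrolled at Washington University, Section 9.1.1 says that "fresh tissue samples will be obtained either by surgical laparoscopic sampling (preferred), endoscopic biopsy, or image-guided core biopsy"; large-volume paracentesis or thoracentesis is allowed at the PI's discretion. The tissue is for the PDX/PDO research. Inclusion criterion 3 sets the timing: "Biopsy or other procedures should be performed at least 7 days prior to C1D1". Section 9.1.1 and calendar footnote 7 make this conditional on safety and feasibility.

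**Other channels.** Section 7.1.2 and Appendix D send unanticipated problems involving risk to participants to HRPO and QASMC, with no link to dosing. Notification of the drug supplier under Section 7.1.5 covers SAEs in patients receiving study drug. Expedited FDA reporting in Appendix D covers suspected adverse reactions, which Appendix C defines by drug causality.

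**The concern.** The biopsy is the most invasive thing that the protocol asks of patients purely for research, and it comes before the date on which the protocol begins to collect adverse events. No section says how a bleed, perforation, infection or hospital admission caused by it is to be recorded, attributed or reported. The DSM report described in Section 13.0 carries a summary of toxicities that rests on this collection. If the events are not collected, those who oversee the trial have no reliable count of harm from a research procedure that they could stop or change. The most serious events are also the ones most likely to keep a patient from starting treatment, and those patients have the weakest route into the data.

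**Working it through.** The plan gives no figure to reproduce here. The check is a reading of the sections against each other, followed by a scale calculation under stated assumptions.

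**Step 1: the gap in time.** The biopsy stands in the Screening column, screening runs up to 28 days before therapy (Section 10.0), and the biopsy is to be done at least 7 days before C1D1. About 7 to 28 days therefore lie between the biopsy and the opening of the routine window.

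**Step 2: where a biopsy complication would go.**

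| Course of the complication | Routine window (7.0, 7.1.6) | Other route in the documents | Result |
|---|---|---|---|
| Begins and resolves before C1D1 | Outside | Perhaps the Screening assessment in the calendar; the baseline-AE sentence may not reach an event that is over | Not reliably recorded |
| Stops the patient from starting | Never opens | Screening assessment, or the unanticipated-problem route if the event qualifies | Not reliably recorded; patient is outside the Section 5.3 population |
| Still present at C1D1 | Began outside | Baseline AE on the Toxicity Form (11.1) | Recorded as a baseline condition; no rule for attribution to the procedure |
| First appears after C1D1 | Inside | Not needed | Recorded; no stated category for the research procedure |

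Section 7.1.6 adds, within its guidance on laboratory values, "Please note that medical history data is not required to be entered on the AE case reporting form". That gives no help in getting a resolved pre-treatment event onto the form.

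**Step 3: patients who do not start.** Section 3.2 excludes patients with grade 3-4 GI bleeding within 3 months, perforation within 6 months, or a serious or nonhealing wound within 28 days, each counted back from enrollment. If the biopsy comes before enrollment, such a complication makes the patient a screen failure. Section 4.0 requires registration before any protocol intervention. If the biopsy follows registration, a patient who becomes too unwell to start is registered but never dosed. On either order, no rule ensures that the event is counted.

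**Step 4: scale.** The documents state neither the number of biopsies, n, nor a complication rate, p; both are assumptions. The value n = 10 is borrowed from the 10 paired samples in Section 15.5, which is a count of paired model samples and not of biopsies; n = 20 shows the effect of doubling it. The chance of at least one complication is 1 − (1 − p)^n.

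| p (assumed) | n = 10 | n = 20 |
|---|---|---|
| 1% | 1 − 0.99^10 = 9.6% | 1 − 0.99^20 = 18.2% |
| 3% | 1 − 0.97^10 = 26.3% | 1 − 0.97^20 = 45.6% |
| 5% | 1 − 0.95^10 = 40.1% | 1 − 0.95^20 = 64.2% |
| 10% | 1 − 0.90^10 = 65.1% | 1 − 0.90^20 = 87.8% |

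Zero events in 10 biopsies would leave a one-sided 95% upper limit of 1 − 0.05^(1/10) = 25.9%. The reason to collect is therefore to see the individual events, since the numbers are too small for a useful rate.

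**The case against.** The strongest reply is that the pre-treatment period is not blank. Section 11.1 takes baseline AEs, the calendar as extracted has an AE assessment at Screening, and an unanticipated problem has its own route whether or not a drug was given. A reader might infer from Section 7.0 alone that biopsy harms are never counted; these places show that the documents do not support that. What remains is narrower. The X may come from a merged cell in the original table. A baseline entry describes a condition at the start of treatment and is not a count of harm from a procedure. The unanticipated-problem route, by its terms, need not take a known procedural complication, although the institutional policies that decide this are not in the documents.

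A reader might also infer that biopsy complications will be mistaken for ramucirumab toxicity. Hemorrhage, perforation and impaired wound healing are indeed ramucirumab risks named in Section 1.5, and Section 6.1.4 ties a treatment rule to bleeding judged possibly related to ramucirumab. But AEs are recorded whatever their relation to drug, an investigator may judge one unrelated, and the eligibility rules on bleeding, perforation, wounds and resolution of surgical toxicity limit carry-over. Misattribution is a possibility and no more.

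Nor is the drug-toxicity objective biased by leaving out patients who were never dosed. Section 2.2 asks about the toxicity of irinotecan plus ramucirumab, and treated patients are the right population for that.

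Finally, nothing firm can be said about the attribution choices on the Toxicity Form, which is not in the documents. The Appendix E sheet asks only about study treatment, but it is for secondary sites, while the biopsies are at Washington University. The DSMB charter is not available either and might add to what the board sees.

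**Conclusion.** The point holds as a gap in the stated collection window. Followed as written, Sections 7.0 and 7.1.6 and the first sentence of Section 11.1 start after the research biopsy, Appendix C does not mention study procedures, and a complication that resolves before C1D1 or prevents treatment is not reliably recorded or attributed. The baseline-AE sentence in Section 11.1 and the Screening entry in the calendar conflict with that window and do not close the gap.

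The size is modest. It concerns a conditional procedure at one of five institutions and leaves the PFS analysis untouched. Under assumed complication rates of 1% to 10%, the chance that at least one such event occurs is about 10% to 65% with 10 biopsies and 18% to 88% with 20. Both the rates and the numbers of biopsies are assumptions. Because the events are harms from a research-only procedure and the change is cheap, the plan should be amended.

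**What to change.** - In Sections 7.0, 7.1.6 and 11.1, collect procedure-related AEs and SAEs from the research biopsy onward for every patient who has one, whether or not treatment starts.
- Extend the Appendix C definition to events associated with study procedures.
- Make sure that the form used at Washington University offers research procedure as an attribution.
- Show these events as a separate line in the DSM report of Section 13.0, with the number of patients biopsied as the denominator.
- Reconcile the calendar row in Section 10.0 and the baseline-AE sentence in Section 11.1 with Sections 7.0 and 7.1.6.
- Leave the Section 5.3 toxicity population as treated patients, so that drug toxicity and procedural harm remain separate questions.

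The cost is amendment wording, one form field and a few extra records at one site. No added procedure or visit is needed.
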